4.3 Justification for dose

The dose range of oral NNC0385-0434 to be investigated in this trial has been selected based on the results from the FHD trial (NN6434-4493) and on modelling data for the expected exposure response and dose response.

Based on modelling analyses of the preliminary data from the FHD trial, the oral NNC0385-0434 dose of 100 mg/day is expected to have an exposure level lower than the exposure seen in the FHD trial s.c. 250 mg single dose arm for up to 6 weeks. The steady state exposure (C_{max}) in a dosing interval of the 100 mg/day dose is predicted to be 32 times lower than the exposure achieved in the s.c. 250 mg dose arm in the FHD trial. This is due to the relatively high s.c. dose investigated in the FHD trial (250 mg), the long half-life of NNC0385-0434 (10.5 days) and the predicted bioavailability of the oral dose (approximately 1% relative to s.c. dosing).

Moreover, no adverse findings were found in toxicity studies of up to 13-week duration in rats and the NOAEL was established as the highest dose administered (12 mg/kg/day s.c. + 50 mg/kg/day orally) at an exposure > 100 fold higher than the expected human exposure at 15-100 mg daily oral dose. Also, no adverse findings were found in local tolerance study after daily oral dosing of 100 mg NNC0385-0434 for 14 weeks in cynomolgus monkeys.

Oral NNC0385-0434 administered as once daily doses of 15, 40 and 100 mg are expected to be within the therapeutically relevant range. This dose range is expected to provide exposures to cover the exposure-response profile with mean LDL-C responses ranging from -28 to -60% change from baseline.

In summary, the exposure expected from simulated data for the oral NNC0385-0434 100 mg once-daily arm is lower than the exposure reached in the FHD trial. Oral doses of 15, 40 and 100 mg NNC0385-0434 are expected to be within the therapeutically relevant range and modelling predictions suggest corresponding LDL-C reductions of approximately 28, 46 and 60% from baseline, respectively.

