- ii. Diagnosed with type 2 diabetes mellitus
4. Serum LDL-C ≥ 1.8 mmol/L (≥ 70 mg/dL) as measured by the central laboratory at screening.
For Japan only: See [Table 5-1](#) for serum LDL-C inclusion criteria for Japanese patients.
5. Patients must be on maximally tolerated dose of statins (see Appendix 7 (Section [10.7](#))).
6. Patients not receiving statin must have documented evidence of intolerance to all doses of at least two different statins (see Appendix 7 (Section [10.7](#))).
7. Patients on any lipid-lowering therapies must be on a stable dose for ≥ 30 days before screening with no planned medication or dose change during study participation (for maximally tolerated statin dose, see Appendix 7 (Section [10.7](#)); for other lipid-lowering therapies, see Section [6.5](#)).

Inclusion criteria for PK sub-study (in addition to inclusion criteria 1-7)

8. For Japanese patients only: Both parents of Japanese descent and from Japanese site
9. For non-Japanese patients only: Both parents of non-Japanese descent and from non-Japanese site

Table 5-1 Inclusion criterium 4 (serum LDL-C) only for Japanese patients**Japanese patients aged ≥ 40 years with established ASCVD defined as at least one of the following:**

History of coronary heart disease defined as at least one of the following¹:

1. Prior myocardial infarction.
2. Prior coronary revascularization (PCI, CABG)
3. $\geq 50\%$ stenosis in a major epicardial coronary artery documented by cardiac catheterisation or CT coronary angiography.
4. Coronary heart disease with ischaemia documented by stress test with any imaging modality.

Serum LDL-C ≥ 2.6 mmol/L (≥ 100 mg/dL)

History of cerebrovascular disease defined as at least one of the following:

1. Ischemic Stroke.
2. Prior carotid artery revascularisation procedure (surgical or endovascular).
3. $\geq 50\%$ stenosis in carotid artery documented by X-ray angiography, MR angiography, CT angiography or Doppler ultrasound.

Serum LDL-C ≥ 3.1 mmol/L (≥ 120 mg/dL)

History of peripheral artery disease in the lower extremities defined as at least one of the following:

1. Current symptoms of intermittent claudication and an ankle-brachial index (ABI) < 0.85 or toe-brachial index (TBI) < 0.7 , both at rest.
2. Current symptoms of intermittent claudication and $\geq 50\%$ stenosis in lower extremity artery documented by X-ray angiography, MR angiography, CT angiography or Duplex ultrasound.
3. Lower extremity artery revascularization procedure.

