6.7 Treatment after end of trial

After the end of trial (visit 10) the patient will continue suitable standard of care at the discretion of the investigator. The patients will not receive treatment after the end of treatment.

7 Discontinuation of trial treatment and subject discontinuation/withdrawal

Treatment of a patient may be discontinued at any time during the trial at the discretion of the investigator for safety, behavioural, compliance or administrative reasons.

Efforts must be made to have the patients attend and complete all scheduled visit procedures. Only patients who withdraw consent will be considered as withdrawn from the trial. Patients must be educated about the continued scientific importance of their data, even if they discontinue trial product.

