8.11 Immunogenicity assessments

Anti-drug antibody samples will be collected according to the flowchart ([Table 1-1](#)). All samples must be drawn prior to trial product administration if trial product administration is planned on the sampling day.

Assessment of antibodies against NNC0385-0434 (anti-drug antibodies) in serum will be performed at Novo Nordisk A/S.

For details on blood sampling, serum preparation and storage, please refer to the laboratory manual.

Analysis for anti-drug antibodies in patients treated with NNC0385-0434 will be done as listed in the flowchart ([Table 1-1](#)) with a binding anti-drug antibody assay. Positive samples will be further characterised for neutralising activity by correlation to PK and PD (with a validated LDL-C assay) i.e. the highly sensitive PD marker LDL-C. Any potential clinical effect of ADAs will be evaluated by correlation to PK, efficacy and safety parameters. Detailed description of the anti-drug antibody assay methods will be included in an analytical report. Antibody assays will be validated according to international guidelines and recommendations. Furthermore, samples will be banked for possible future analysis in a dedicated neutralising anti-drug antibody analysis if this assay would be deemed necessary (for further details, see Section [10.6.2](#)).

Results from the binding anti-drug antibody analyses from visit 2, 4, 6, 8, 9 and 10 will be available at the end of trial.

At the end of the trial, the following data will be electronically transferred to the Novo Nordisk database:

- Anti-NNC0385-0434 binding antibodies (positive/negative)
- Anti-NNC0385-0434 binding antibodies cross-reacting with endogenous EGF-A (positive/negative)
- Anti-NNC0385-0434 binding antibody titre (no unit)

Patients who have tested positive for antibodies against NNC0385-0434 (high titre of antibodies) at visit 10 (end-of-trial visit) will be requested to have a follow-up analysis performed 12 months after visit 10. If the anti-NNC0385-0434 antibody titre has not declined at the follow-up analysis, the patient may be requested to have an additional follow-up analysis performed. The result from additional follow-up analyses will be reported in a separate analytical report. Thus, the results will not be part of the CTR.

The investigator will not be able to review the results of antibody measurements in relation to AEs as these will be analysed after LPLV.

Refer to Section [10.6.2](#) for further details.

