10.2 Appendix 2: Clinical laboratory tests

- The tests detailed in [Table 10-1](#), [Table 10-2](#) and [Table 10-3](#) will be performed by the central laboratory unless otherwise noted.
- Additional tests may be performed at any time during the trial as determined necessary by the investigator or required by local regulations. Only laboratory samples specified in the protocol should be sent to the central laboratory for analysis; if additional laboratory sampling is needed, e.g. to follow up on AEs, this must be done at a local laboratory.
- The central lab will communicate to the investigator abnormal values of parameters not requested in the protocol but identified by the laboratory equipment and/or their processes according to their lab SOPs. These data will not be transferred to the trial database. The investigator should review such values for AEs and report these according to this protocol.
- The investigator must review all laboratory results for concomitant illnesses and AEs.
- Laboratory samples will be destroyed no later than at finalisation of the CTR, except for the following:
- Human biosamples for retention will be stored as described in Appendix 6 (Section [10.6](#)).
- For haematology samples (differential count) where the test result is not normal, then a part of the sample may be kept for up to two years or according to local regulations.

Table 10-1 Protocol-required efficacy laboratory assessments

Laboratory assessments	Parameters
Lipids	
 • Lipoprotein a (Lp(a)) • Apolipoprotein B (ApoB) • Apolipoprotein C III (ApoCIII) • Total cholesterol • High density lipoprotein (HDL) cholesterol • Low density lipoprotein (LDL) cholesterol • Very low density lipoprotein (VLDL) cholesterol • Triglycerides
Target engagement	
 • PCSK9 levels^a
NOTES:	
^a Analysis performed by special laboratory contracted by Novo Nordisk	

Table 10-2 Protocol-required safety laboratory assessments

Laboratory assessments	Parameters
Haematology	
 • Lymphocytes • Eosinophils • Basophils • Monocytes • Neutrophils • Haematocrit • Mean corpuscular haemoglobin, concentration • Mean corpuscular volume • Reticulocytes • Haemoglobin • Erythrocytes • Leukocytes • Thrombocytes

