Biochemistry ^a	
 • Bicarbonate Serum • High Sensitive C-Reactive Protein • eGFR Using CKD-EPI Formula (Chronic Kidney Disease Epidemiology Collaboration) • Aspartate Aminotransferase • Albumin • Urea • Calcium • Sodium • Potassium • Creatinine • Alkaline Phosphatase • Alanine Aminotransferase • Gamma-glutamyl transferase (GGT) • Bilirubin • Creatine Kinase • Lactate plasma
Coagulation parameters	
 • Prothrombin Time • INR
Pregnancy Testing	
 • Highly sensitive serum human chorionic gonadotropin (hCG) pregnancy test^b
Glucose metabolism	
 • Fasting plasma glucose • HbA1_c
Antibodies	
 • Anti NNC0385-0434 Antibodies^c

Notes:

^a Details of required actions and follow-up assessments for increased liver parameters including any discontinuation criteria are given in Section 10.3 (Hy's Law) and Section 7.1.

^b Only applicable for female patients who have stopped menstruating within the last 5 years (Appendix 4 (Section 10.4))

^c Analysis performed at Novo Nordisk A/S

Table 10-3 Protocol-required PK assessments

Laboratory assessments	Parameters
Pharmacokinetics	
• NNC0385-0434 plasma concentrations^a

Notes:
^a Analysis performed by special laboratory contracted by Novo Nordisk

Laboratory results that could unblind the trial (e.g. antibodies and PK) will not be reported to the sites until the trial has been unblinded.

10.3 Appendix 3: Adverse events: Definitions and procedures for recording, evaluation, follow-up, and reporting

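### Does the rule on withholding unblinding laboratory results leave post-randomisation LDL-C open to the sites?

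*Protocol*

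**What the plan says.** Section 6.3.2 of the protocol makes the trial double-blind within each oral dose level, active against size-matched placebo; evolocumab is open label. Sections 6.3.2 and 6.3.3 deal with tablet appearance, packaging, code break and which laboratory staff may see the allocation. They do not mention lipid results.

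Appendix 2 (section 10.2) contains the rule on reporting: "Laboratory results that could unblind the trial (e.g. antibodies and PK) will not be reported to the sites until the trial has been unblinded". It also contains a review duty, "The investigator must review all laboratory results for concomitant illnesses and AEs", and an allowance for extra testing, "Additional tests may be performed at any time during the trial as determined necessary by the investigator or required by local regulations", with any additional sampling sent to a local laboratory. Table 10-1 of the appendix lists LDL-C and the other lipids as efficacy assessments. The safety assessments are in a separate table, Table 10-2.

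Section 8.11 says of antibodies that "The investigator will not be able to review the results of antibody measurements in relation to AEs", and gives as the reason that the samples are analysed after the last patient's last visit. The same section calls LDL-C "the highly sensitive PD marker LDL-C".

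Sections 8.2.1 and 8.3.5 refer laboratory conduct to a laboratory manual, which is not among the documents. The SAP is silent on which results sites see.

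**The concern.** The two named examples are antibodies and PK. The result that responds most directly to the drug, LDL-C, is not named, and no sentence elsewhere says whether post-randomisation lipids go to sites. Read literally, the duty to review all results points towards disclosure, and antibodies have an explicit statement that LDL-C lacks. Sites also have a starting value, because the eligibility threshold applies to LDL-C "as measured by the central laboratory at screening". One later value, central or local, would then give an approximate percent change.

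If sites did see lipids, the assay itself would not be biased, since it is run centrally. The risk would lie in investigator judgement:

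- Ratings of adverse event severity and causality (section 10.3.4) feed the placebo-controlled safety objective.
- Section 7 opens with "Treatment of a patient may be discontinued at any time during the trial at the discretion of the investigator". Discontinuation is the only intercurrent event of the primary estimand.
- Background lipid therapy could be adjusted, although section 6.5 requires it to stay unchanged unless a safety concern arises.

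**Working it through.** **Step 1: how informative is one LDL-C change?**

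Inputs:

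- Effects d = 28, 46 and 60 points. Section 4.3: "modelling predictions suggest corresponding LDL-C reductions of approximately 28, 46 and 60% from baseline, respectively".
- SD = 30 points (section 9.2), with 27 and 34 as the range from the two published values quoted there.
- Allocation 3:1, active to matched placebo, within each dose level (section 6.3.1), so always guessing active is right 75% of the time.
- Assumptions not in the documents: mean placebo change 0, normal distributions, equal SD.

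The plan gives no figure on this point. As a check that the SD is read as the plan uses it, the first row of Table 9-1 was reproduced. With 45 per arm, 88 degrees of freedom and half-width 14,

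P = P(χ²₈₈ ≤ 88 × [14 / (1.987 × 30 × √(2/45))]²) = 93.7%, against 94% stated.

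Formulas:

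- Concordance (chance that an active patient shows the larger fall) = Φ(d / (SD√2)).
- Best cut-off: call active if the change is below c = (2·SD²·ln 3 − d²) / (2d).
- Placebo patients correctly called = 1 − Φ(c/SD).
- Overall accuracy = 0.75·Φ((c+d)/SD) + 0.25·[1 − Φ(c/SD)].

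Worked case, 100 mg at SD 30: c = (2 × 900 × 1.0986 − 3600) / 120 = −13.5. Placebo correctly called = 1 − Φ(−0.45) = 0.674. Accuracy = 0.75 × 0.939 + 0.25 × 0.674 = 0.873.

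| | 15 mg | 40 mg | 100 mg |
|---|---|---|---|
| Concordance, SD 30 | 0.745 | 0.861 | 0.921 |
| Cut-off c, SD 30 | +21.3 | −1.5 | −13.5 |
| Accuracy, SD 30 (75% by default) | 77.2% | 82.8% | 87.3% |
| Accuracy, SD 27 | 78.1% | 84.5% | 89.2% |
| Accuracy, SD 34 | 76.4% | 81.0% | 85.1% |
| Placebo correctly called, SD 30 | 24% | 52% | 67% |
| Placebo correctly called, SD 27 | 29% | 58% | 73% |
| Placebo correctly called, SD 34 | 18% | 45% | 60% |

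At SD 30 the gain over guessing is about 2, 8 and 12 percentage points. These are week-12 effects. Visit 9 ends treatment, so a week-12 value cannot prompt discontinuation. Only earlier values could, and those taken before steady state (about week 6, section 4.2) may say less.

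**Step 2: apply the rule to that result.** The Appendix 2 sentence sets a test by function: a result that could unblind is not reported. Antibodies and PK illustrate it and do not limit it. On the figures above, LDL-C meets the test clearly at 40 and 100 mg. At 15 mg the gain in guessing is slight, but a masking rule has to apply to lipids as a class, because the site does not know which patients are on active drug.

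**Step 3: do the other passages override it?**

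- The review duty is limited by its purpose, finding concomitant illnesses and adverse events, and it can apply only to results the site receives. It cannot be literal in any case, since antibodies and PK are withheld.
- The antibody sentence in section 8.11 rests on when the assay is run. It is not a blinding provision, so the lack of a twin for LDL-C implies nothing about release.
- The example given for local sampling is follow-up of adverse events. That discretion would exist whatever Appendix 2 said about central results.

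**Step 4: what would follow if lipids were seen?** The safety endpoint is a count of treatment-emergent events, reported descriptively (SAP sections 5.4.2 and 5.6); severity and causality sort the events within those tables. Patients who stop treatment are still asked to attend visit 9 (section 7.1), and the additional estimand uses their values whether or not they stopped. For the primary estimand, section 9.3 extends the on-treatment period to 58 days after the last dose. By that definition a day-84 value still counts if the last dose was on or after day 84 − 58 = 26. Section 9.2 describes values from patients who stopped early as missing, so this last argument carries little weight.

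**The case for a change.** The best case for a change is that the blind should not depend on inference. The sponsor chose double-blinding within dose level to limit bias and plans a separate group to protect the blind if a safety signal has to be examined (section 10.1.6.1). Against that aim, leaving the primary endpoint out of the list of withheld results, next to an unqualified instruction to review everything, looks careless. Between half and two-thirds of placebo patients at 40 and 100 mg could be identified from a single value at SD 30, and naming lipids would take a few words.

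Much of this stands. The wording is looser than it could be, the arithmetic is right, and no sentence names lipids as withheld. What does not stand is the step from an unnamed example to a hole in the blind. The stronger the case that LDL-C unblinds, the more plainly the existing rule covers it. No passage shows lipids being reported to sites, and the manual that would set the central laboratory's reports has not been seen. Restrictions on local lipid testing, or a separate route for lipid alerts, would go well beyond the ambiguity shown. No effect on adverse event ratings or discontinuation has been estimated.

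**Conclusion.** This is a gap in detail that those applying the rule would fill sensibly. Followed as written, Appendix 2 withholds any result that could unblind, and LDL-C is such a result: on the plan's predicted effects and SD it lifts correct guessing from 75% to 77, 83 and 87%. Those figures assume no mean placebo change, normality, equal SDs and week-12 effects.

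Naming lipids beside antibodies and PK would be a harmless tidying of the text, but it would alter no estimand, analysis, sample size or error rate, and the superiority conclusion is unlikely to depend on it. The conclusion rests on reading the two named results as examples, which is what the wording says, and on there being no sign in the documents that lipids are released. A laboratory manual that sent post-randomisation lipids to sites would contradict the protocol's own rule. That would be a fault in the manual's implementation and would not show a defect in the plan.

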10.3.1 Definition of AE

AE definition

An AE is any untoward medical occurrence in a clinical trial subject that is temporally associated with the use of an investigational medicinal product (IMP), whether or not considered related to the IMP.

An AE can therefore be any unfavourable and unintended sign, including an abnormal laboratory finding, symptom or disease (new or exacerbated) temporally associated with the use of an IMP.

Events meeting the AE definition

- Any abnormal laboratory test results or safety assessments considered clinically significant in the medical and scientific judgment of the investigator, including events that have worsened from prior to the time point from which AEs are collected
- Conditions detected or diagnosed after IMP administration even though it may have been present prior to the time point from which AEs are collected
- Exacerbation/worsening of a chronic or intermittent condition including either an increase in frequency and/or intensity of the condition
- Signs, symptoms or the clinical sequelae of a suspected drug-drug interaction
- Signs, symptoms or the clinical sequelae of a suspected overdose of IMP regardless of intent

Events NOT meeting the AE definition

- Conditions present prior to the time point from which AEs are collected and anticipated day-to-day fluctuations of these conditions, including those identified during screening or other trial procedures performed before exposure to IMP.
- Note: Conditions present or occurring prior to the time point from which AEs are collected should be recorded as concomitant illness/medical history.
- Medical or surgical procedures (e.g. endoscopy, appendectomy). The condition that leads to the procedure is the AE.
- Medical or surgical procedures not preceded by an AE or worsening of a known condition.

10.3.2 Definition of an SAE

An SAE is an AE that fulfils at least one of the following criteria:

a. Results in death

b. Is life-threatening

The term 'life-threatening' in the definition of 'serious' refers to an event in which the patient was at risk of death at the time of the event. It does not refer to an event which hypothetically might have caused death, if it were more severe.

c. Requires inpatient hospitalisation or prolongation of existing hospitalisation

- Hospitalisation signifies that the patient has been detained at the hospital or emergency ward for observation and/or treatment that would not have been appropriate in the physician's office or outpatient setting. Complications that occur during hospitalisation are AEs. If a complication prolongs hospitalisation or fulfils any other seriousness criteria, the event is serious. When in doubt as to whether "hospitalisation" occurred or was necessary, the AE should be considered serious.

- Hospitalisation for elective treatment (e.g. elective medical or surgical procedures) of a condition that was present prior to the time point from which AEs are collected, and that did not worsen, is not considered an AE.

Note:

- Hospitalisations for administrative, trial related, social and convenience reasons do not constitute AEs and should therefore not be reported as AEs or SAEs.
- Hospital admissions for medical or surgical procedures, planned before trial inclusion, are not considered AEs or SAEs.

d. Results in persistent or significant disability/incapacity

- The term disability means a substantial disruption of a person's ability to conduct normal life functions.
- This definition is not intended to include experience of relatively minor medical significance, such as uncomplicated headache, nausea, vomiting, diarrhoea, influenza, and accidental trauma (e.g. sprained ankle), which may interfere with or prevent everyday life functions but do not constitute a substantial disruption.

e. Is a congenital anomaly/birth defect

f. Important medical event:

- Medical or scientific judgment should be exercised in deciding whether SAE reporting is appropriate in other situations. This includes important medical events that may not be immediately life-threatening or result in death or hospitalisation but may jeopardise the patient or may require medical or surgical intervention to prevent one of the other outcomes listed in the above definition. These events should usually be considered serious and reported as SAEs using the important medical event criterion.
- The following adverse events must always be reported as SAEs using the important medical event criterion if no other seriousness criteria are applicable:
 - Suspicion of transmission of infectious agents via the IMP
 - Risk of liver injury defined as alanine aminotransferase (ALT) or aspartate aminotransferase (AST) $>3 \times$ UNL and total bilirubin $>2 \times$ UNL where no alternative aetiology exists (Hy's law)

